6.11.2.2. Analysis of Immunogenicity Related to Covid-19 Vaccination

A demographic table of study subjects who received Covid-19 vaccination will be provided including:

- number and percentage of subjects having pre-vaccination antibody assessment
- number and percentage of subjects having post-1st vaccine regimen assessment
- number and percentage of subjects having post-1st booster assessment
- number and percentage of subjects having post-2nd booster assessment
- number and percentage of subjects having post-3rd booster assessment
- age at time of 1st vaccination
- sex
- exposure (years) to ponesimod at time of 1st vaccination
- number and percentage of subjects in different vaccine type of the 1st vaccine regimen
- number and percentage of subjects with or without evidence of Covid-19 infection prior to 1st vaccine regimen
- number and percentage of subjects in different categories of lymphocyte count In the above frequency tabulations, percentage is calculated based on number of subjects in Covid-19 Vaccine Analysis Set.

For S-ELISA and N-ELISA assays, the following results will be presented:

- N, geometric mean and corresponding 95% CI of the actual values of pre-vaccination, post-first vaccine regimen, post-first, post-second and post-third booster. Note that the analysis by timepoint will be performed only if more than 5 subjects have antibody concentration measured at that timepoint.
- Dot plots with dots for subject values with the corresponding geometric mean, 95% CI, minimum and maximum for each assay, for pre-, post- 1st vaccine regimen, post- 1st booster and post- 2nd booster will be presented. In the graphs, values in BAU/ml unit will be displayed on the log10 scale. Note that the analysis by timepoint will be performed only if more than 5 subjects have antibody concentration measured at that timepoint.
- The above analyses will be repeated for S-ELISA antibody concentrations for the following subgroups: vaccine type of the 1st vaccine regimen, evidence of Covid-19 infection prior to 1st vaccine regimen and categories of lymphocyte count. Box plot will be generated to visualize S-ELISA antibody concentrations for the above-mentioned subgroups. Note that the analysis by timepoint will be performed only if more than 5 subjects have antibody concentration measured at the timepoint.

Analyses of S-ELISA and N-ELISA antibody concentration will be presented in BAU/ml unit only.

For the calculation of the geometric mean and its corresponding 95% CI, the arithmetic mean and its corresponding 95% CI are calculated on the log10 transformed values. These values are backtransformed to provide the geometric mean and its corresponding 95% CI.

A listing containing assessment date, timepoint related to each vaccination and value of S-ELISA and N-ELISA assessment antibody concentration will be provided.

A listing of Covid-19 vaccinations will be provided.

6.11.3. Analysis of Adverse Events Related to Covid-19 Vaccination

A summary table will be provided for the following Covid-19 infection AEs for the Covid-19 Vaccine Analysis Set:

- (i) any Covid-19 infection AEs.
- (ii) any Covid-19 infection serious AEs.
- (iii) any Covid-19 infection AEs sorted by severity (mild, moderate, severe).
- (iv) any Covid-19 infection AEs leading to treatment discontinuation.
- (v) any Covid-19 infection AE leading to death.

For each of the above, summary tables will include overall, and the following time-points:

- (vi) any Covid-19 infection AEs prior to 1st dose of vaccination
- (vii) any Covid-19 infection AE post 1st dose (Day 1) of vaccination

AE listing will include age at time of vaccination, days since 1st dose of vaccination, start and end dates, AE preferred/reported term, vaccine PT and AE severity.

6.12. Appendix 12 Study visit and assessment schedule

Table 12 and Table 13 show a schematic representation of the assessments during the extension study

Table 12: Visit and assessment schedule

Periods	Name	AC-058B	301 (core study)	AC-058B303 (extension study) TREATMENT PERIOD									
	Duration		NA	Treatme	Treatment may continue until 240 weeks or until ponesimod is commercially available (whichever occurs first)								
	Number		NA	1	2	3	4	5	6, 8-10, 12-14, 16- 18, 20-22	7, 11, 15, 19	23		
Visits	Name	FU1 Core Study	Abbreviated FU2 Core Study (1)	Enrollment	W2	W4	W12	W24	W36, W60, W72, W84, W108, W120, W132, W156, W168, W180, W204, W216, W228	W48, W96, W144, W192	ЕОТ		
									Every 12 w	veeks	W240 or		
	Time	NA	NA	Day 1(2)	Day 15	Week 4	Week 12	Week 24		Every 48 weeks	earlier (14)		
	Visit window	NA	NA	NA	-1 to +3 days	±7 days	±7 days	±14 days	±14 days	±14 days	14 days		
Informed c				X									
Inclusion/e	xclusion criteria*			X									
Demograph				X									
Medical Hi	story*			X									
EDSS/FS*				X			X	X	X	X	X		
Relapse*		X	X	\leftarrow			Χ (3)			\longrightarrow		
SDMT*				`			X	X		X	X		
MSFC*										X	X		
SF-36**								X		X	X		
eC-SSRS*	*									X	X		
MRI**(15)										X	X		
Concomita	nt medications*	X	X	X	X	X	X	X	X	X	X		
	camination*			X				X		X	X		
Dermatolog	gical examination* (4)									X	X		
Body weig										X	X		
Body temp	erature*	X		X	X	X	X	X	X	X	X		
Systolic/dia	astolic blood pressure*(5)	X		X(5)	X	X	X	X	X	X	X		
12 Lead EC		X		X						X	X		
Pulse rate*	``				X	X	X	X	X				
Ophthalmo	logical examination / OCT						X	X		X	X		
Pulmonary	function tests* (8)	X				X				X	X		
	y/Chemistry**	X			Х	\leftarrow	(9)	\rightarrow	X	X	X		
Urinalysis*		X			1	`		X	X	Х	X		
Pregnancy	test*/** (10)	X		X	1	X	X	X	X	X serum	X serum		
Elimination	n procedure compliance	X	X	-	İ	·-							
	ide plasma concentration			X (11)									
Additional serology*	serum sample for viral			X									
Study treat	ment dispensing &			X	X	х	х	X	X	X	Х		
AEs* / SAl		X	X	X	X	X	X	X	X	X	X		

- * Data collected in the eCRF
- ** Electronically transferred to the sponsor

Day 1 (date of treatment start) is to be used as the reference date for the purpose of calculating the subsequent visit dates (and time windows).

- 1) This visit will only take place if the compliance with the teriflunomide elimination procedure in the core study was not sufficient and has to be re-assessed prior to the study drug administration on Day 1.
- 2) Visit 1 includes a pre-treatment period which lasts from signing of the informed consent until first dosing of study treatment. Ideally, all assessments and procedures of Visit 1 (e.g., signing of the informed consent, first study treatment dosing and post-dose cardiac monitoring) should occur on the same day as the core study FU1 or abbreviated FU2 (whichever applies). In all cases, informed consent should be signed no later than one day after FU1 or FU2 visit (whichever applies) and all assessments and procedures of Visit 1 must be completed (i.e., study treatment start) no longer than 7 days after signing of the informed consent. The date of Day 1 corresponds to the date of the first dose of study treatment in the extension study. The investigator should make every effort to minimize the duration between EOT of the core study and Day 1 of the extension study. Ideally the treatment interruption should last no longer than 15 days.
- 3) At every study visit, subjects are reminded to contact their principal investigator / treating neurologist at the clinical site immediately in the event of the appearance of any new or worsening neurological symptoms. In addition, the site will contact the subject 6 weeks (± 7 days) after each visit starting with Visit 4 (Week 12) in order to proactively inquire about any new or worsened neurological symptoms. Whenever, between visits, a subject experiences any new or worsening neurological symptoms, he/she must contact the principal investigator / treating neurologist, study nurse or clinical coordinator as soon as possible in order to complete a relapse assessment questionnaire [see protocol appendix 10].
- 4) Dermatological examination to be performed by a dermatologist.
- 5) Systolic / diastolic blood pressure: Only pre-dose except Day 1. On Day 1 pre-dose and hourly (± 15 min) for at least 4 hours post-dose and up to 12 hours.
- 6) ECGs: Only pre-dose except Day 1. On Day 1 pre-dose and hourly (± 15 min) for at least 4 hours post-dose and up to 12 hours.
- 7) OCT and/or ophthalmological examination to be performed at any visit in the presence of visual symptoms suggestive of macular edema or active uveitis.
- 8) PFTs including spirometry to be performed in all subjects; DL_{CO} to be performed in a subset of subjects at selected sites only.
- 9) Monitoring of hematology/chemistry every 4 weeks for the first 24 weeks after enrollment (±7 days).
- 10) Between visits, urine pregnancy tests are done every 4 weeks (± 7 days) at home. At all visits, the methods of contraception will be reviewed and the contraceptive method form entered in the eCRF must be updated as applicable.
- 11) Blood sample for a teriflunomide test (results to be communicated to site only if needed, e.g., in the case of AEs where the measurement of exposure to teriflunomide is of relevance).
- 12) Scheduled study medication dispensing/return procedures may be adapted according to the site practice. No medication dispensed at EOT.
- 13) All AEs and SAEs that occur after signing the informed consent and up to 30 days after study treatment discontinuation (i.e., EOS) must be reported.
- 14) The EOT Visit will take place at Week 240 or earlier if ponesimod becomes commercially available in the subject's country or the subject prematurely discontinues from the study. In all cases, the EOT visit should take place 1 day after the last dose of study treatment but no later than 14 days after the last dose of study treatment.
- 15) In case of premature study treatment discontinuation, the MRI assessment at EOT does not need to be performed if the EOT visit occurs within 4 weeks of the MRI assessment at Visits 7, 11, 15, or 19 (Weeks 48, 96, 144, or 196).
- AE = adverse event; DL_{CO} = diffusing capacity of the lungs, measured using carbon monoxide; ECG = electrocardiogram; eCRF = electronic Case Report Form; eC-SSRS = electronic self-rated version of the Columbia-Suicide Severity Rating Scale; EDSS = expanded disability status scale; EOS = End-of-Study; EOT = End-of-Treatment; FS = Functional System; FU = follow-up; MRI = magnetic resonance imaging; MSFC = Multiple Sclerosis Functional Composite; NA = not applicable; OCT = optical coherence tomography; PFT = pulmonary function test; SAE = serious adverse event; W = week.

Table 13: Visit and assessment schedule (Part 2)

Periods	Name	FOLLOW-UP	DW-UP UNSCHEDULED							
	Duration	30 Days								
Visits	Number	24	R1, R2,	U1, U2,	I1, I	2,		P1, P2,	(9)	
					D1	D15				
	Name	EOS	Relapse	Unscheduled (8)	Re-initiation D1	Re-initiation D15	Interruption / planned pregnancy	Eligibility for re- initiation / planned pregnancy	Re-initiation D1 / pregnancy	Re-initiation D15 / pregnancy
					Day 1 of re- initiation	Day 15 of re- initiation	Unscheduled visit after drug interruption for planned pregnancy	Unscheduled visit prior to study drug re-initiation after interruption for planned pregnancy	Unscheduled visit following study drug interruption for planned pregnancy for re-start	Unscheduled visit following study drug interruption for planned pregnancy for re-start
	Time	Last study treatment intake + 30 days	Any day between Day 1 and EOS	Earliest after Visit 5 (Week 24) and until 6 weeks after the first of two consecutive tests showing teriflunomide plasma level < 0.02 mg/L and at least 30 days after study treatment discontinuation	30 days (± 5 days) days before study drug re-initiation					
	Visit window	+14 days	+7 days	NA	NA	± 1 day	± 7 days	NA	NA	NA
EDSS/FS*		X	X	X			X	X		
Relapse*		X	X	X(11)	X(11)	X(11)	X(11)	X	X	X(11)
MRI**				X			X	X		
Concomita	nt medications*	X	X	X	X		X	X	X	
,	kamination*		X	X			X	X		
	gical examination*			X			X			
Body weig				X			X	X	X	
Body temp		X	X	X	X	X	X	X	X	X
	astolic blood pressure*	X	X	X	X(1)	X	X	X	X(1)	X
12 Lead E		X		X	X(2)	X	X	X	X(2)	X
Pulse rate*			X	X(12)			X(12)			
Ophthalmo (3)	ological examination/OCT*	X		X			X	X		
Pulmonary	function tests* (4)	X		X			X	X		
Hematolog	y/Chemistry**	X		X			X	X		
Urinalysis'		X		X			X	X		
	nide plasma concentration (5)			X						
Viral serol	ogy			X						
Pregnancy		X serum		X			X serum	X urine (first assessment)	X (first assessment; 10)	

Study treatment dispensing & accountability (6)*			X	X	X			Х	X
AEs*/ SAEs* (7)	X	X	X	X	X	X	X	X	X

^{*} Data collected in the eCRF.

Day 1 (date of enrollment visit) is to be used as the reference date for the purpose of calculating the subsequent visit dates (and time windows).

- 1) SBP/DBP: Pre-dose and hourly (± 15 min) for at least 4 hours post-dose and up to 12 hours.
- 2) ECGs: Pre-dose and hourly (± 15 min) for at least 4 hours post-dose and up to 12 hours.
- 3) OCT and/or ophthalmological examination to be performed at any visit in the presence of visual symptoms suggestive of macular edema or active uveitis.
- 4) PFTs include spirometry to be performed in all subjects; DLco to be performed in a subset of subjects at selected sites only.
- 5) Teriflunomide plasma concentration may be assessed at Week 19 ± 7 days and at Week 21 ± 7 days and may be repeated at Visit 5 (Week 24) and at following visits if necessary until two consecutive test results confirming plasma concentration of teriflunomide < 0.02 mg/L are available.
- 6) Scheduled study medication dispensing/return procedures may be adapted according to the site practice.
- 7) All AEs and SAEs up to 30 days after study treatment discontinuation must be reported.
- 8) Unscheduled visits may be performed at any time during the study and the indicated assessments are optional, based on the judgment of the investigator.
- 9) The wish to become pregnant and stay in the study must be communicated by the female subject to the principal investigator / treating neurologist during a scheduled visit. Interruption of study treatment for planned pregnancy may only take place after Visit 5 (Week 24) and at earliest 6 weeks after the first of two consecutive tests confirming plasma teriflunomide level < 0.02 mg/L and at least 30 days after ponesimod interruption.
- 10) Review and assess contraception methods and total duration of study treatment interruption, which should not exceed 81 weeks.
- 11) Only if the subject is meeting the principal investigator / treating neurologist at unscheduled visits.
- 12) Only if no 12-lead ECG is performed at this visit.
- AE = adverse event; DBP = diastolic blood pressure; DL_{CO} = diffusing capacity of the lungs, measured using carbon monoxide; ECG = electrocardiogram; EDSS = expanded disability status scale; EOS = End-of-Study; FS = Functional System; I = re-initiation visit; HR = heart rate; MRI = Magnetic resonance imaging; OCT = Optical coherence tomography; P = pregnancy visit; PFT = pulmonary function test; R = relapse visit; SAE = serious adverse event; SDMT = Symbol Digit Modalities Test; SBP = systolic blood pressure; U = unscheduled visit.

^{**} Electronically transferred to the sponsor

6.13. Appendix 13 Handling of missing/incomplete date and the time fields

In the following, 'lower limit' and 'upper limit' refer to the minimum or maximum, respectively, of a possible date. For example, if the day is missing, the lowest limit is the first day of the given month and the upper limit is the last day of the given month. If the day and month are missing, the lower limit refers to the first day of the given year and the upper limit to the last day of the given year. The earliest and the latest dates refer to the first or last date, respectively, when ordered in sequence.

6.13.1. Previous / Concomitant therapies

For previous and concomitant therapies with missing or partial start and end dates the following rules for assignation to previous therapies and study concomitant therapies are applied [see Table 14].

Table 14: Handling of missing or partial start and end dates for previous/concomitant therapies

eCRF	Analysis	Start date	End date	Previous /
page	Period			Concomitant
Prev*	Combined Analysis Period	Unless start date clearly after/on core STS (Start date either: prior to core STS date, partial with either lower or upper limit prior to core STS date, or missing)	Unless end date after/on core STS (Either prior core STS, partial with either lower or upper limit prior core STS, or missing)	Previous
Con**	Combined Analysis Period	Unless start date clearly after/on core STS (as above)	Prior to core STS date; or Partial with upper limit prior to core STS date;	Previous
Con**	Combined Analysis Period	Start date confirmed prior core STS (Start date either: prior to core STS date, partial with upper limit prior to core STS date)	End date on core STS date and 'Ongoing at start of Treatment' ticked 'No'; or Partial with lower limit prior to core STS date and upper limit after/on core STS date and 'Ongoing at start of Treatment' ticked 'No';	Previous
Con***	Extension Analysis Period	Unless start date clearly after/on extension STS (Start date either: prior to extension STS date, partial with either lower or upper limit prior to extension STS date, or missing)	Prior to extension STS date; or Partial with upper limit prior to extension STS date;	Previous
Con***	Extension Analysis Period	Start date confirmed prior extension STS (Start date either: prior to extension STS date, partial with upper limit prior to extension STS date)	End date on extension STS date and 'Ongoing at start of Treatment' ticked 'No'; or Partial with lower limit prior to extension STS date and upper limit after/on extension STS date and 'Ongoing at start of Treatment' ticked 'No';	Previous

CONFIDENTIAL – FOIA Exemptions Apply in U.S.

Any	Combined/Exte	All other cases not listed above	All other cases not listed	Treatment
	nsion Analysis		above	concomitant
	Period			

Con = concomitant; eCRF = electronic Case Report Form; MS = multiple sclerosis; Prev = previous; STS = study treatment start. For subjects randomized but not treated in the core study the randomization date is used instead of the core STS. For subjects enrolled but not treated in the extension study, the enrollment date is used instead of the extension STS.

Concomitant medications entered on the eCRF page "Ongoing Concomitant Medication from AC-058B301" are considered to be concomitant in both the Combined and Extension Analysis Periods. Concomitant medications entered as "Ongoing at EOS" on the core study eCRF page are considered to be concomitant in both the Combined and Extension Analysis Periods for subjects that entered the extension, even if a corresponding "Ongoing Concomitant Medication from AC-058B301" has not been completed for the extension.

In this study subjects are allowed to switch to commercial ponesimod prior to week 240 / week 288, with the ponesimod medication documented in the concomitant medication eCRF page. In this regard, the commercial ponesimod is considered as post-EOT medication unless there is evidence showing that the commercial ponesimod is taken prior to EOT date. In case of partial CM start date, the commercial ponesimod is considered as a post-EOT medication if the month and/or year is the same as the EOT date. The commercial ponesimod is considered as a post-EOT medication in case of completely missing start date in the CM dataset.

6.13.2. Relapse Start Date

For the analysis of ARR in the Extension Analysis Period, the start date of the confirmed relapse as entered on the eCRF by the treating neurologist must be within the interval of [extension enrollment date; extension EOS].

For the analysis of ARR in the Combined Analysis Period, the start date of the confirmed relapse as entered on the eCRF by the treating neurologist must be within the interval of [date of randomization; extension EOS].

All confirmed relapses from randomization in the core study up to the EOS visit in either core or extension studies for all subjects in the FAS will be used in the analysis of the ARR endpoint regardless of study treatment compliance; therefore, no data will be excluded from the analysis.

Every effort will be made to collect relapse information as completely as possible, with a focus on collecting all start dates and all EDSS/FS data required for the relapses to make a correct evaluation of relapse confirmation. All relapses with missing or incomplete start dates will be included in the efficacy analysis, unless it is clear that they have occurred prior to the start of the Analysis Period.

Type of date/time	Analysis Period	Date/time is incomplete	Date/time is missing
Relapse start date (collected on 'Relapse Summary' eCRF)	Core/Combined Analysis Period	Maximum of lower limit and randomization date Unless upper limit is prior to randomization date, then upper limit	Randomization date (for relapse reported in the core study) or enrollment date (for relapse reported in the extension study)

CONFIDENTIAL - FOIA Exemptions Apply in U.S.

^{*} Includes core study core eCRF forms 'Previous Medications' or 'MS Specific Treatment History Log': On these forms as per CRF completion guidelines only medications that stopped prior to signature of informed consent are to be recorded.

^{**} Includes all core study eCRF forms collecting therapies apart from 'Previous Medications' or 'MS Specific Treatment History Log eCRF.

^{***} Includes extension eCRF forms 'Concomitant Medications' and extension eCRF form 'Study-concomitant Therapy – Disease-modifying for MS'.

Type of date/time	Analysis Period	Date/time is incomplete	Date/time is missing
Relapse start date (collected on 'Relapse Summary' eCRF)	Extension Analysis Period	Maximum of lower limit and enrollment date Unless upper limit is prior to enrollment date, then upper limit	Enrollment date

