1.2.2. Pre-treatment period

The pre-treatment period includes all pre-dose assessments of Visit 1 and starts when the subject completes the core study FU visits FU1 or FU2 (whichever applies) and signs the informed consent. This will be considered as the enrollment into the extension study. The pre-treatment period ends with the first dose of study treatment (i.e., Day 1). The pre-treatment period must not last longer than 7 days (i.e., signing of the informed consent until study treatment initiation ≤ 7 days).

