5. STATISTICAL ANALYSES

5.1. General Considerations

5.1.1. Analysis Periods

5.1.1.1. Extension Analysis Period

This period includes all available data collected on or after the date of first intake of ponesimod treatment in the extension study, through the extension EOS for efficacy variables, or the last treatment date in the extension study + 15 days for safety variables.

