5.1.9.1. Extension enrollment date

The extension enrollment date is the date when the subject signed the Informed Consent Form and is taken directly from RAVE.

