5.3. Analysis of efficacy variables

5.3.1. Definition of Endpoint(s)

5.3.1.1. Relapse-related variables

5.3.1.1.1. Annualized Relapse Rate (ARR)

The ARR is defined as the number of relapses per subject-year.

The ARR will be calculated for both confirmed relapses and for all relapses, for both the Combined and the Extension Analysis Periods.

To evaluate the ARR for both the Combined and the Extension Analysis Periods, the following variables will be derived per subject and Analysis Period:

- Number of all relapses (confirmed and unconfirmed) from start date of the Analysis Period up to the end of Analysis Period;
- Number of confirmed relapses from start date of the Analysis Period up to end of analysis;
- Length of observation expressed in years, defined as: (Analysis Period end date Analysis Period start date of + 1) in days, divided by 365.25.
- Logarithm of the length of observation during Analysis Period as derived above.

Additionally, for the Core Analysis Period, the following ARR related variables from the core study will be included in the ADaM dataset as derived in the core study:

- Number of confirmed relapses from date of randomization in the core up to core EOS;
- Length of observation during the core study expressed in years, defined as: [core EOS date date of randomization in the core + 1] in days, divided by 365.25;

Additionally, the number of confirmed relapses and length of observation time will be derived per 24-week time period, separately for the Core and the Extension Analysis Periods, for the following time periods:

Core Analysis Period

- Core Week 0-24: \geq Core Day $1 \leq$ Core Day 168;
- Core Week 24-48: > Core Day 168 ≤ Core Day 336;
- Core Week 48-72: > Core Day 336 ≤ Core Day 504;
- Core Week 72-96: > Core Day 504 ≤ Core Day 672;
- Core Week 96-EOS: > Core Day 672 ≤ Core EOS;

Extension Analysis Period

- Extension Week 0-24: ≥ Extension Day 1 ≤ Extension Day 168;
- Extension Week 24-48: > Extension Day 168 ≤ Extension Day 336;
- Extension Week 48-72: > Extension Day 336 ≤ Extension Day 504;
- Extension Week 72-96: > Extension Day 504 ≤ Extension Day 672;

•

- Extension Week 96-120: > Extension Day 672 ≤ Extension Day 840;
- Extension Week 120-144: > Extension Day 840 ≤ Extension Day 1008;
- Extension Week 144-168: > Extension Day 1008 ≤ Extension Day 1176;

_

- Extension Week 168-192: > Extension Day 1176 ≤ Extension Day 1344;
- Extension Week 192-216: > Extension Day 1344 ≤ Extension Day 1512;

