5.3.2.2.2. Additional analyses of ARR

All relapses will be analyzed for the Combined Analysis Period on the FAS and EXTS as described in Section 5.3.2.1.1, i.e., including the first summary table described (and adding the ARR estimate and 95% CI from a NB model).

This approach will also be used to analyze confirmed relapses on:the Extension Analysis Period using the EXTS and the EXTS and for all relapses on:

• the Extension Analysis Period using the EXTS;

with the logarithm of the appropriate observation time during the related period as an offset variable.

Additionally, for confirmed relapses, the ARR estimate and 95% CI from a Poisson model (as the NB model is not expected to converge for all time periods) will be determined by 24-week period (as defined in Section 5.3.1) using FAS and EXTS as follows. The log of observational time during each interval will be used as offset.

- Core Analysis Period (core weeks 0-24, 24-48, 48-72, 72-96, 96-core EOS);
- Extension Analysis Period (extension weeks 0-24, 24-48, 48-72, 72-96, 96-120, 120-144, 144-168, 168-192, 192-216, 216-Extension EOS).

A line plot will be created to present the ARR estimate and the corresponding 95% CI by 24 weeks period.

Relapse characteristics will be summarized using descriptive statistics for the Combined Analysis Period on the FAS and for the Extension Analysis Period on the EXTS. This includes the following:

- Number (%) of subjects with at least one: relapse, relapse requiring hospitalization, relapse treated with corticosteroids; for all relapses up to EOS/cut-off and for confirmed relapses up to EOS/cut-off.
- Number (%) of relapses (out of total number of relapses) requiring hospitalization, treated with corticosteroids and descriptive statistics for continuous data for relapse duration (days); for all relapses up to EOS as well as for confirmed relapses up to EOS.

Full details of all relapses will be presented in a listing.

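### The SAP gives two start dates for counting relapses in the Extension ARR: first dose (5.1.1.1, 5.3.1.1.1) and enrollment (6.13.2)

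*SAP*

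**What the plan says.** Two parts of the SAP set the start of the relapse count for the Extension ARR.

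- **Period and endpoint definition.** Section 5.1.1.1 defines the Extension Analysis Period: "This period includes all available data collected on or after the date of first intake of ponesimod treatment in the extension study". Section 5.3.1.1.1 defines the count as "Number of confirmed relapses from start date of the Analysis Period up to end of analysis". It derives the observation time from the same period dates ("Length of observation expressed in years, defined as: (Analysis Period end date" minus the period start date, plus one day). Section 5.3.2.2.2 fits the extension model "with the logarithm of the appropriate observation time during the related period as an offset variable". The first extension interval is "Extension Week 0-24: ≥ Extension Day 1 ≤ Extension Day 168", and Extension Day 1 is the first ponesimod administration in the extension.
- **Date-handling appendix.** Section 6.13.2 requires that the start date of a confirmed relapse "must be within the interval of [extension enrollment date; extension EOS". Its table sets a wholly missing start date to the enrollment date. It sets a partial date to the later of its lower limit and the enrollment date, unless its upper limit is before enrollment.

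Section 5.1.9.1 states: "The extension enrollment date is the date when the subject signed the Informed Consent Form". Section 1.2.2 limits the distance from consent to first dose: "The pre-treatment period must not last longer than 7 days".

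**The concern.** A rate needs events and person-time from the same window. Under 5.3.1.1.1 they match. Under 6.13.2 the events can start up to 7 days before the person-time does. Two programmers working from the same SAP could therefore derive different extension counts.

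Relapses dated in those days are also off treatment. Core follow-up visits FU1 and FU2 fall 14-22 and 23-37 days after the last core dose (1.2.1), and extension consent follows completion of that visit (1.2.2). Counting such relapses would add off-drug events to a rate read as relapse activity on extension ponesimod.

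There is also a reconciliation problem. The overall extension ARR and the ARR by 24-week interval are both planned for confirmed relapses. If one counts from enrollment and the other from Day 1, their totals can differ without explanation.

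**Working it through.** The SAP states no ARR or relapse count on this point, so there is no figure to reproduce. The check compares dates and then bounds the effect.

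**Start dates side by side**

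| Element | Starts at | SAP section |
|---|---|---|
| Extension Analysis Period | first dose | 5.1.1.1 |
| Relapse count, endpoint definition | period start = first dose | 5.3.1.1.1 |
| Observation time and offset | period start = first dose | 5.3.1.1.1, 5.3.2.2.2 |
| First extension 24-week interval | Extension Day 1 = first dose | 5.3.1.1.1 |
| Relapse count window | enrollment (consent) | 6.13.2 |
| Earliest imputed date for an undated relapse | enrollment (consent) | 6.13.2 |

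**Imputation (illustrative dates).** Take consent on 10 May and first dose on 15 May.

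- Relapse recorded only as May: max(1 May, 10 May) = 10 May, which is before Extension Day 1.
- Relapse recorded only as June: max(1 June, 10 May) = 1 June, inside the period and unaffected.
- Start date wholly missing: 10 May.

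Only wholly missing dates, and partial dates that span enrollment, move to enrollment.

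**Where the pre-dose days fall.** The last core interval ends at core EOS and the first extension interval begins at Day 1. With the full 7-day gap:

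- Consent on the core EOS day: 7 days lie in the 6.13.2 window before Day 1. One is the core EOS day, which belongs to the last core interval. The other 6 belong to no interval.
- Consent one day after core EOS: all 7 days belong to no interval.

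The one bridging rule in 5.3.1.1.1 applies when core EOS is recorded after the extension treatment start. It resets core EOS to the day before Day 1. It does not cover core EOS falling before Day 1.

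**Size.** Share of follow-up = gap days / observation days, taking EOS at 30 days after last dose:

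- 240 weeks: 7 / (1680 + 30) = 7 / 1710 = 0.41%
- 96 weeks: 7 / (672 + 30) = 7 / 702 = 1.0%
- 48 weeks: 7 / (336 + 30) = 7 / 366 = 1.9%

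Upper bound on uncounted person-time, if all 877 enrolled subjects (section 3) had the full gap: 877 × 7 / 365.25 = 16.8 subject-years.

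Expected relapses in the gap = 16.8 × relapse rate. The SAP gives no rate, so a range of 0.1 to 0.5 per subject-year is **assumed**:

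| Assumed rate | 7-day gap, all subjects | 1-day gap, all subjects |
|---|---|---|
| 0.1 | 1.7 | 0.2 |
| 0.2 | 3.4 | 0.5 |
| 0.3 | 5.0 | 0.7 |
| 0.5 | 8.4 | 1.2 |

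With same-day consent and dosing, the result is 0.

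**The case against.** The strongest reply is that 5.3.1.1.1 is the endpoint definition and already counts relapses from the period start, so numerator and denominator agree there. This stands. A reader might infer from 6.13.2 alone that the Extension ARR simply is counted from enrollment and is biased upward. The SAP does not support that. It holds two rules, and bias arises only if 6.13.2 is followed.

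Two further readings go too far.

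- A reader might infer that every missing or partial relapse date goes to enrollment and becomes an off-drug event without person-time. Partial dates in later months do not go there. A relapse reported in the extension with an unknown date probably occurred after first dose, since at most 7 pre-dose days stand against up to 240 weeks on treatment. Section 6.13.2 deliberately keeps such relapses unless they clearly precede the Analysis Period. For these the problem is interval placement, and the person-time argument applies only to relapses actually dated before first dose.
- A reader might infer that every such relapse falls outside all intervals. One dated on or before core EOS falls in the last core interval.

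It can also be said that 5.3.2.1.1 describes the offset as time in study, and that 5.2.1.10 measures time in the extension from enrollment, which would match 6.13.2. But 5.3.1.1.1 gives the definition specific to ARR, and time from enrollment would still leave the 24-week intervals starting at Day 1.

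Finally, the consequence is slight. The Extension ARR is an additional analysis, all analyses are exploratory (section 2), and the visit schedule in 6.12 treats same-day consent and dosing as ideal. This is a fair limit on importance, but it does not reconcile the two rules.

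**Conclusion.** The contradiction is real and minor. Sections 5.1.1.1 and 5.3.1.1.1 start the extension count and time at first dose, while 6.13.2 starts the count and the imputation at enrollment. If 6.13.2 governs, relapses dated between consent and first dose enter without person-time. Relapses dated or imputed before Extension Day 1 then enter the overall extension count but no extension interval.

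The mismatch is 0 to 7 days per subject. The person-time figures are ceilings, because they give every enrolled subject the maximum gap. The expected relapse counts rest in addition on an assumed rate. The main ARR analysis is untouched, since in the Combined Analysis Period both the relapse window and the observation time start at randomization.

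**What to change.** 1. In 6.13.2, for the Extension Analysis Period, replace the extension enrollment date with the date of first extension dose (Extension Day 1), in both the inclusion window and the imputation table. This agrees with 5.3.1.1.1. It also agrees with the adverse-event rule in 6.13.3.1, which anchors imputation at first extension dose and uses enrollment only when that date is missing.
2. In the Core/Combined row of the same table, use the same date for a wholly missing start date of a relapse reported in the extension, so that one relapse does not carry two imputed dates.
3. State that relapses between core EOS and Extension Day 1 are counted in the Combined Analysis Period only and not in the 24-week intervals. Step 1 alone would leave these relapses unassigned.

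The cost is wording in one section and a matching change to the relapse derivation. No data collection or model changes.
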